Aim 3: To compare postoperative rates of surgical site infection (SSI) in women who receive chlorhexidine gluconate versus povidone iodine vaginal antiseptic preparation preoperatively, defined as per CDC guidelines (described below). **Hypothesis:** Chlorhexidine gluconate will demonstrate a non-inferior rate of postoperative SSI compared to povidone iodine.

Aim 4: evaluate vaginal and vulvar irritation for post groups on postop day 1 as measured by a 5-point vaginal irritation scale previously used in a safety and tolerability study examining vaginal chlorhexidine gluconate (Al Niaimi et al) **Hypothesis:** Chlorhexidine gluconate will demonstrate a non-inferior rate of postoperative vaginal and vulvar irritation for postop day 1.

2. Background

Steady improvements have been made in surgical infection control over the past century including improved instrument sterilization methods, operating room ventilation, surgical barriers including gowns and drapes, surgical technique, preoperative antimicrobial prophylaxis, and preoperative cleaning or prepping of the surgical site. Despite these advancements, UTIs and SSIs continue to be a common cause of postoperative morbidity.

Urinary Tract Infections are one of the most common post-operative complications associated with urogynecologic surgery. One study estimated that 33% of women develop UTIs in the 12 week period following surgical treatment for stress urinary incontinence (Anger et al). UTIs are associated with increased health care costs, antibiotic resistance, and morbidity and mortality for patients. Because UTIs are so common, they are used as a quality metric and tracked by the Joint Commission, the Centers for Medicare and Medicaid Services (CMS), and National Surgical Quality Improvement Program (NSQIP), among others.

Another concern following pelvic surgery (which may include a vaginal approach or surgery on the vagina) is development of surgical site infections (SSI). A recent study found that SSIs were among the most common healthcare-associated infection, accounting for 31% of all healthcare-associated infections (HAI) among hospitalized patients. (Magill 1) Vaginal surgery is classified as clean-contaminated procedures because of the natural bacterial flora of the vagina. This generally increases infection risk over clean procedures.

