The primary outcome of this study is to determine rates of urinary tract infections in the period 2 weeks post-surgery for both cohorts. For the purposes of this study, UTI has been defined in section 1 (objectives), aim 1. We have powered the study based on a 10% difference in UTI rates between groups within 2 weeks of surgery. Based on a non-inferiority study design and a between group difference of less than or equal to 10%, we need 58 patients per group (chlorhexidine gluconate versus povidone iodine) to detect no difference with an alpha =0.05 and with 80% power. Assuming a high dropout rate of 20%, we will enroll a total of up to 200 patients (100/group), or until we reach our primary endpoint of 2 week follow up for 116 patients, or 58 patients in each group. We have increased the numbers due to COVID-19 and loss to follow-up.

This is not a multi-center study. Data will be housed at the Eubank clinic.

6. Study Timelines

Timeline	May 2019- April 2020	May 2020-Sept 2020
Subject recruitment, therapy, through 3 month follow up	x	x
Data analysis		x
Manuscript preparation		x

Over the past 12 months, 318 urogynecology cases were performed at UNM and SRMC. Assuming a conservative estimate of 50% enrollment, recruitment of up to 200 patients would be feasible over the next 3 month period.. Since subjects will be followed for 6 weeks after surgery, it may take up to 14 months to collect 6 weeks of follow up data. We estimate that data analysis, manuscript preparation and publication will take an additional 10 months.

7. Study Endpoints

The **primary endpoint** of our study is to determine the incidence of urinary tract infections within weeks of surgery in women who undergo pelvic surgery (which may include a vaginal approach or surgery on the vagina) with either chlorhexidine gluconate or povidone iodine vaginal antiseptic preparation. Our **secondary endpoints** are to investigate SSI rates in the two groups at 6 weeks, and vaginal irritation on the first postoperative day.

Given the extremely low-risk nature of the therapeutic interventions, we do not have any **safety endpoints**. However, any patients noted to have an allergic response will be treated according to the normal standard of care depending on the severity of their allergic reaction.

8. Research Setting

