 - c. an abscess or other evidence of infection involving the organ/space that is detected on gross anatomical or histopathologic exam, or imaging test evidence suggestive of infection. AND meets at least one criterion for a specific organ/space infection site.

13. Data Analysis

Data Analysis: Between and within group differences will be evaluated using Wilcoxon-Mann-Whitney test for categorical variables and t-tests for continuous variables. If there are any baseline differences between groups, a multivariate analysis will determine the contribution of these differences to observed differences (if any) between groups.

Power Analysis: Power analysis was performed based on previously reported rates of postoperative urinary tract infection after urogynecologic surgery as well as rates of relative reduction in infection with chlorhexidine presurgical preparations as opposed to povidone iodine. To achieve significance for a non-inferiority study using these assumptions we would need 116 patients, 58 per group to detect this difference with $\alpha = 0.05$ and with 80% power.

To allow for a dropout or loss to follow up of 20% due to the pandemic, we will enroll at least 200 patients.

Comparative Cost Analysis

The cost analysis will be conducted from patient and health system perspective and will be expressed as incremental cost required to prevent one episode of UTI.

Direct and indirect cost of health care utilization will be obtained when episodes of UTI occur, including the patient reported travel expenses and copays to obtain care, cost of UTI diagnosis with urine dipstick, urinalysis, and urine culture standardized to University of New Mexico Health Sciences Center institutional pricing as well as the cost of antibiotics for treatment.

14. Provisions to Monitor the Data to Ensure the Safety of Subjects

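### Aims 3 and 4 hypothesise non-inferiority for SSI and day-1 irritation without a margin, and the planned tests of difference cannot support such a conclusion

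*Combined protocol and SAP*

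**What the plan says.** Section 1 (Objectives) gives each of these secondary aims a non-inferiority hypothesis. Aim 3: "Chlorhexidine gluconate will demonstrate a non-inferior rate of postoperative SSI compared to povidone iodine". Aim 4: "Chlorhexidine gluconate will demonstrate a non-inferior rate of postoperative vaginal and vulvar irritation for postop day 1". The Aim 4 outcome is described "as measured by a 5-point vaginal irritation scale previously used in a safety and tolerability study examining vaginal chlorhexidine gluconate"; no cut-point on that scale is given.

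Section 5 (Number of Subjects) contains the only figure that could serve as a margin, and it belongs to the primary outcome: "We have powered the study based on a 10% difference in UTI rates between groups within 2 weeks of surgery". The sample size follows: "Based on a non-inferiority study design and a between group difference of less than or equal to 10%, we need 58 patients per group", "to detect no difference with an alpha =0.05 and with 80% power". Enrolment may reach 100 per group, with 20% dropout assumed. Section 7 (Study Endpoints) lists SSI at 6 weeks and irritation on the first postoperative day as secondary endpoints.

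For the analysis, Section 13 says: "Between and within group differences will be evaluated using Wilcoxon-Mann-Whitney test for categorical variables and t-tests for continuous variables". It adds a multivariate analysis if the groups differ at baseline. It names no confidence interval, shifted null hypothesis or decision rule for SSI or irritation.

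**The concern.** A non-inferiority hypothesis is a statement about a margin: the excess risk with CHG is smaller than some prespecified amount. Without the margin there is nothing to test. A test of difference addresses another null hypothesis, that the arms are equal, and failing to reject it does not show that any particular excess has been ruled out. With few events, failing to reject is the usual result whether or not CHG is worse.

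Aim 4 has a further gap. It refers to a rate, but the measure is an ordinal score, so the quantity to be compared is undefined.

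The stakes are practical. Section 2 says povidone iodine (PI) is the only FDA-approved agent for vaginal surgery, that some institutions restrict vaginal CHG, and that non-inferiority has not been studied for UTI or SSI in this setting. A reported finding of SSI non-inferiority would speak directly to that gap. Sections 7 and 14 provide no safety endpoints and no DSMB, so SSI and irritation are the main planned comparisons of harm after UTI.

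**Working it through.** **1. The plan's own figure.** No sample size or power is stated for SSI or irritation. The 58 per group is for UTI. For non-inferiority of two proportions with margin d,

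n per group = (z_alpha + z_beta)² × [p1(1 − p1) + p2(1 − p2)] / (d − (p2 − p1))², with p1 for PI and p2 for CHG.

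The control rate and the sidedness of alpha are not stated, so 58 cannot be derived from the text. With d = 0.10 and equal rates:
- p = 4.9%, one-sided 0.05: (1.645 + 0.842)² × 2 × 0.049 × 0.951 / 0.01 = 57.6, so 58.
- p = 3.8%, one-sided 0.025: 58.
- p = 33%, the only UTI rate cited (over 12 weeks, not 2): 274 (one-sided 0.05) or 348 (one-sided 0.025).

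It is also matched by 20% with PI and a 44% relative reduction with CHG at one-sided 0.025: 2.802² × (0.2 × 0.8 + 0.112 × 0.888) / 0.188² = 57.6. Whichever was used, the calculation concerns UTI and lends no margin to SSI or irritation.

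**2. Numbers per arm.** 58 is the target with 2-week follow-up; 100 is the enrolment ceiling per group; 100 × (1 − 0.20) = 80 is that ceiling after the assumed dropout.

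**3. Chance of a non-significant SSI test when CHG doubles the risk.** The documents give no SSI rate, so PI rates of 2%, 5% and 10% are assumptions. For each pair of event counts I took the binomial probabilities under p (PI) and 2p (CHG), and summed those pairs for which the two-sided 0.05 tie-corrected Wilcoxon-Mann-Whitney test on the yes/no outcome is not significant.

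| Assumed SSI risk, PI to CHG | 58 per arm | 80 per arm | 100 per arm |
|---|---|---|---|
| 2% to 4% | 93% | 90% | 89% |
| 5% to 10% | 83% | 79% | 73% |
| 10% to 20% | 69% | 58% | 48% |

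The pooled z test is nearly but not exactly equivalent, because the tie-corrected Wilcoxon variance carries a factor N/(N − 1), N being the total in both arms. At 10% to 20% and 58 per arm it gives 67.0% against 68.5%. The probability crosses 50% at a PI rate of about 15%, 12% and 10% for 58, 80 and 100 per arm.

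**4. Precision for SSI.** The half-width of the 95% interval for the risk difference at a common rate p is 1.96 × √(2p(1 − p)/n). At n = 58:
- 2%: 1.96 × √(0.0392/58) = 5.1 points
- 5%: 1.96 × √(0.095/58) = 7.9 points
- 10%: 1.96 × √(0.18/58) = 10.9 points

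**5. What a margin would require for SSI.** Formula of step 1, equal rates, 80% power, one-sided 0.05 (0.025 in brackets), n per arm:

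| Assumed SSI rate | Margin 2 points | 3 points | 5 points | 10 points |
|---|---|---|---|---|
| 2% | 606 (770) | 270 (342) | 97 (124) | 25 (31) |
| 5% | 1469 (1865) | 653 (829) | 235 (299) | 59 (75) |

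Borrowing the 10-point UTI margin is no remedy at low rates. With a true doubling from 2% to 4%, the upper confidence limit would fall below 10 points with probability 0.81 (0.66) at 58 per arm and 0.93 (0.86) at 100.

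**6. Irritation.** Without a cut-point, doubling the risk has no meaning here. If any irritation were treated as yes/no, a doubling from 20% to 40% would be non-significant with probability 34%, 20% and 12% at 58, 80 and 100 per arm. The SSI result therefore does not carry over.

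**The case against.** The strongest reply is that the plan nowhere says a p-value above 0.05 will be read as non-inferiority. That is correct. Section 13 gives no rule at all, so a reader who infers that the protocol prescribes this rule goes further than the text. What stands is narrower: the listed tests offer no other route to the stated hypotheses, apart from a significant result in favour of CHG.

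A reader might also infer that a doubling of harm would probably go unnoticed on both outcomes. The documents do not support that. For irritation they give neither a rate nor a cut-point, and at moderate rates a doubling would usually be detected. For SSI the statement depends on assumed rates and on the number analysed: at 10% to 20% with 100 per arm it is no longer more likely than not. At 2% to 5% it holds across 58 to 100 per arm (73% to 93%).

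Nor is it shown that this design could never support a non-inferiority claim. A 5-point SSI margin at a 2% rate needs 97 per arm at one-sided 0.05, just inside the ceiling of 100, although above the 80 left after the assumed dropout. Nothing shows that Aim 4 would be out of reach once its endpoint and margin were defined. Deleting the hypotheses is therefore one option, not the only one.

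Finally, these are secondary aims, which limits the weight of the point. It does not remove it, because a hypothesis of non-inferiority is stated for each.

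**Conclusion.** The point holds in a limited form. Whatever the event rates, three defects stand: no margin for SSI or irritation, no defined rate for irritation, and an analysis by tests of difference, which cannot establish non-inferiority.

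The size can be given for SSI only, and only under assumed rates. If CHG doubled the SSI risk from 2% or 5%, a two-sided 0.05 test would be non-significant 73% to 93% of the time over 58 to 100 per arm; from 10%, about 48% to 69%. For irritation no size is claimed. Since the matter concerns secondary aims and wording can settle it, it should be corrected, but it does not bear on the primary sample size.

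**What to change.** Restate Aims 3 and 4 as estimation. For SSI at 6 weeks, report the risk difference with a 95% interval. For irritation, report the score distribution by arm and the Mann-Whitney probability (or the mean difference) with a 95% interval. State in Section 13 that no non-inferiority conclusion will be drawn from a non-significant test on these outcomes.

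If the sponsor prefers to keep a non-inferiority claim, prespecify and justify a margin for each outcome, define the irritation endpoint (a cut-point, or a difference in score), and judge the claim by the confidence interval against the margin. For SSI, margins of 2 to 3 points at assumed rates of 2% to 5% need about 270 or more per arm, so this choice probably means a wider margin or an acknowledged lack of power.

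The first option costs only wording and no additional patients; the sponsor gives up two secondary claims. The second keeps the claims, but they would have to be qualified.

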We will perform a single masked, non-inferiority randomized-controlled trial to compare the effectiveness of chlorhexidine gluconate and povidone iodine pre-surgical vaginal antiseptic cleaning preparations prior to pelvic surgery (which may include a vaginal approach or surgery on the vagina). The target population are those patients presenting for urogynecologic surgery in the University of New Mexico health system. Participants will be masked as they will not be informed regarding which intervention they receive while under anesthesia at the start of their scheduled procedure. All women will give written or verbal consent prior to enrollment. It is not feasible to mask the surgeon, as the two antiseptic preparations are colored differently which is evident throughout surgery.

4. Inclusion and Exclusion Criteria

We will recruit patients who present to the University of New Mexico (UNM Women's Care Eubank Clinic or Sandoval Regional Medical Center) with urogynecologic conditions requiring pelvic surgery (which may include a vaginal approach or surgery on the vagina). Patients will receive usual care including evaluation of prior medical history and physical exam, any necessary diagnostic studies and preoperative workup. All patients will be offered typical treatment options regardless of their desire to participate in the research study.

Patients will be enrolled if they meet the inclusion and do not meet the exclusion criteria.

The inclusion criteria are:

- Female Subjects >18 years of age
- English or Spanish speaking/reading
- Must be able to provide informed consent.
- Undergoing urogynecologic procedures or surgery at UNM, OSIS, or SRMC

Exclusion criteria:

- Pregnant - all patients are verified regarding pregnancy status prior to gynecologic surgical intervention at all sites of surgery within the UNM system –

for patients who are premenopausal and have a uterus, a urine pregnancy test is administered in the preoperative setting. Pregnancy status is also determined prior to this in the office setting by interview and patient provided history prior to offering surgery to the patient.

- Inability to return for follow-up visits
- No concurrent need for vaginal antiseptics, such as cases of sacral neuromodulation
- Lack of telephone
- Known allergy to either antiseptic agent
- Prisoners will not be eligible to participate in this study

5. Number of Subjects

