The study will be performed at the University of New Mexico Hospital (UNMH), Sandoval Regional Medical Center (SRMC) and University of New Mexico Outpatient Surgery and Imaging Services OSIS, and all associated urogynecology clinics. Potential subjects will be recruited in the UNM Eubank and SRMC clinics. All patients will have a complete history and physical taken. They will undergo a pelvic exam and will undergo typical preoperative diagnosis and workup performed as part of the standard of care for their respective urogynecologic diagnosis. After recruitment, they will undergo the consent process, and fill out initial questionnaires in the outpatient offices or by phone. All other follow-up will be performed in the above-mentioned outpatient clinics.

There are no laboratory tests in this trial other than what would routinely be collected for the workup of urogynecologic conditions or postoperative infections or complications. As we are essentially comparing two standard treatment options we do not think community advisory board is necessary. There will not be any research conducted outside of the UNM HSC and its affiliates.

9. Resources Available

[name] is a board certified subspecialist in Urogynecology and will serve as the primary investigator (PI) for this study. In addition, Drs. [name] and [name] will also help oversee and mentor [name] with this study; they are both very experienced researchers. All have been PIs on multiple research trials and has successfully completed and published many studies. [name] is a Female pelvic medicine and reconstructive surgery (urogynecology) fellow. He has the time and resources including 12 months of protected research time, to complete this study.

The University of New Mexico (UNM) urogynecology division evaluates patients primarily in two outpatient clinics. UNM Eubank Urogynecology Clinic located in Northeast Albuquerque provides a full range of services for women with pelvic floor disorders. The Eubank clinic consists of 8 examination rooms, 2 treatment rooms, and 2 physical therapy rooms. Our second location is at Sandoval Regional Medical Center (SRMC), a community-based facility located in Rio Rancho, New Mexico, a large suburb located north of Albuquerque.

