If a patient demonstrates an allergic reaction to either antiseptic (povidone iodine or chlorhexidine gluconate), they will be routinely treated for allergic symptoms and informed of the antiseptic type, the allergy will also be added to their medical record.

Table 1: Outcomes collected at various time points

	Baseline	2 weeks	6 weeks
Demographic and medical history	X		
Follow up questionnaire	X	X	X
Vaginal irritation questionnaire	Postop day 1		

Our primary outcome is to report the rates of postoperative urinary tract infections for each cohort at 2 weeks postoperatively. It is our standard of care to see patients back at 2 weeks and 6 weeks following surgical management of urogynecological conditions.

If patients are unable to follow up in clinic as standard care, telephone communication may be used to ask patients if they have received care at an outside facility for urinary tract infection or other infection related to surgical treatment.

Outcome Measures:

- Urinary tract infection (UTI): Patients with >100k colony forming units on urine culture, symptomatic patients with >10k colony forming units on urine culture or reported UTI symptoms resulting in empiric treatment without urine culture.**
- Surgical Site Infection (SSI): Surgical site infection as defined by the below criteria in the 6 week postoperative period.**

- 1) We will categorize SSI based on CDC criteria (ref) adapted from the CDC guidelines as referenced below. We will record SSI events 6 weeks after surgery.
 - a. CDC Criterion: Surgical Site Infection (SSI)
 - i. Superficial incisional SSI must meet the following criteria:
 1. Date of event for infection occurs within 6 weeks after any operative procedure (where day 0 is the procedure date)
 2. AND involves only skin and subcutaneous tissue of the incision
 3. AND patient has at least one of the following:
 - a. Purulent drainage from the superficial incision.
 - b. Organisms identified from an aseptically-obtained specimen from the superficial incision or subcutaneous tissue by a culture or non-culture based microbiologic testing method which is performed for purposes of clinical diagnosis or treatment (for example, not Active Surveillance Culture/Testing (ASC/AST).

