There is no DSMB that will be monitoring safety of these procedures. Both vaginal antiseptic preparations are routinely used preoperatively for surgery for urogynecologic conditions. Additionally, we will keep track of any adverse events and ask patients about adverse events on either the operative or postoperative day, as well as at the 2 week and 6 week follow up visits. Because neither of the studied treatments are experimental and are already widely used, we do not anticipate an above average risk of adverse events; overall risk is minimal. Participants will have access to a 24/7 phone number to reach research or clinical staff with any concerns. All adverse events will be recorded and reported to the study PI.

We do not anticipate any conditions that would trigger a suspension or termination of the research study.

15. Withdrawal of Subjects

Any participant may withdraw from the study at any time without penalty and will continue to receive the clinical standard of care. A subject may be withdrawn from the study without her consent at the discretion of the physician and study staff if they believe she no longer meets study inclusion criteria or if she meets exclusion criteria, or if they believe that it is not in her best interest to continue study participation. Investigators may withdraw a subject if the subject is not following the study protocol. If a participant is withdrawn from the study either at her own discretion or that of the research staff, she may continue with management of her urogynecologic condition in the usual fashion.

To minimize withdrawal from the study, patients will be randomized in the preoperative anesthesia care unit (PACU) on the day of surgery. We will follow CONSORT guidelines (Shultz 2010), and analyze all participants assessed for eligibility within the study. We will document reasons for withdrawal from the study including failure to meet eligibility criteria or participant

declining enrollment into the study. The withdrawal procedure is clearly documented in the study consent.

If a patient withdraws from the study, the research team will not be required to destroy or retrieve any health information that has already been used or shared prior to when withdrawal is received.

16. Data Management/Confidentiality

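### Section 15 lets staff withdraw a randomised woman for meeting an exclusion criterion, with no time limit, so one who later cannot attend clinic may be removed although a telephone call could still obtain much of her 2-week UTI outcome

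*Combined protocol and SAP*

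**What the plan says.** Section 4 (Inclusion and Exclusion Criteria) lists "Inability to return for follow-up visits" and "Lack of telephone" among the exclusions. Its lead-in places the criteria at entry: "Patients will be enrolled if they meet the inclusion and do not meet the exclusion criteria".

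Section 8 (Research Setting), after describing recruitment, consent and the first questionnaires, says: "All other follow-up will be performed in the above-mentioned outpatient clinics".

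Section 12 (Study Procedures) schedules the follow-up questionnaire at 2 and 6 weeks and adds: "If patients are unable to follow up in clinic as standard care, telephone communication may be used". The question asked on the call is whether she has had care elsewhere for a UTI or another infection related to the surgery.

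Section 15 (Withdrawal of Subjects) allows a woman to be withdrawn even if she has not agreed to it, and words the rule thus: "at the discretion of the physician and study staff if they believe she no longer meets study inclusion criteria or if she meets exclusion criteria". It gives a second route: "Investigators may withdraw a subject if the subject is not following the study protocol". Neither route carries a time limit. The same section places randomisation on the day of surgery and says that everyone assessed for eligibility will be analysed.

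**The concern.** Inability to attend at 2 or 6 weeks can only show itself after randomisation, because the envelope is opened on the day of surgery. By then a woman who cannot travel back fits the wording of an exclusion criterion, and section 15 makes that wording a ground for removing her. Section 12 allows her to be telephoned but does not require it.

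Two things are at stake. The first is completeness. Aim 1 counts symptoms treated empirically as a UTI, and section 12 asks about treatment elsewhere, so the plan itself expects some non-attenders to have events that the clinic would not see. The second is bias. The discretion is exercised after allocation by people who may know the arm: section 3 says the surgeon cannot be masked, and section 16 has a research coordinator open the envelope. Removing women with UTI from the chlorhexidine arm pushes the result towards non-inferiority. Removing them from the povidone iodine arm pushes it the other way.

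**Working it through.** The plan gives no figure on this point, so the main check is a reading of the sections together.

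**1. Sections 4 and 12 alone.** Section 4 governs who is enrolled. Section 12 covers patients who turn out to be unable to come to clinic. The telephone exclusion in section 4 fits a planned back-up call. These provisions are compatible.

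**2. Adding section 15.** One ground for withdrawal is that a woman no longer meets the inclusion criteria, which implies that eligibility can be re-judged after entry. The companion ground, meeting an exclusion criterion, has no time point. Applied as written to a randomised woman who cannot return, it permits withdrawal.

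**3. Adding section 8.** If all later follow-up is in clinic, a woman who does not attend could also be regarded as not following the protocol, which is the second withdrawal route.

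**4. Which rule prevails?** No section says. The same woman may be
- telephoned and kept (section 12),
- withdrawn for meeting an exclusion criterion (sections 4 and 15), or
- withdrawn as off-protocol (sections 8 and 15).

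**5. Does the analysis plan settle it?** Section 15's statement that everyone assessed for eligibility will be analysed leans towards keeping her. But neither section 13 nor section 15 defines an intention-to-treat or per-protocol set, or says how a withdrawn woman's outcome is counted.

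**6. How much could a few removals matter?** This is an illustration only.
- Inputs from section 5: 58 women per group and a 10-point difference, used here as the margin.
- Assumed: a 2-week UTI rate of 10% to 33%. The plan states no such rate. The 33% is the 12-week figure after incontinence surgery cited in section 2, used as an upper value.
- Formula: shift = x/n − (x − k)/(n − k), where x is the number of UTIs in the arm, n = 58, and k women with UTI are removed.

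| Assumed rate | x of 58 | k = 1 | k = 3 |
|---|---|---|---|
| 10% | 6 | 6/58 − 5/57 = 10.34% − 8.77% = 1.57 points | 6/58 − 3/55 = 10.34% − 5.45% = 4.89 points |
| 33% | 19 | 19/58 − 18/57 = 32.76% − 31.58% = 1.18 points | 19/58 − 16/55 = 32.76% − 29.09% = 3.67 points |

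Three such removals confined to one arm would use roughly a third to a half of the 10 points.

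**7. Is the target number at risk?** Section 5 enrols up to 200 women or until 116 have 2-week follow-up. The tolerable loss is (200 − 116)/200 = 84/200 = 42%, well above the planned 20%. The issue is who is removed, not whether 116 can be reached.

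**The case against.** The strongest reply is that the provisions are coherent when read in the ordinary way: exclude at entry those who already know that they cannot return, and telephone those who become unable to later. Section 15 is permissive, its stated aim in randomising on the day of surgery is to limit withdrawals, and the reasons for withdrawal it says it will document are entry-stage ones. A natural use of the exclusion-criterion clause is a positive pregnancy test on the day of surgery. Participants are masked, and nothing suggests that inability to travel differs by arm.

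Most of this stands. It shows that removal is not directed and may never have been intended. It does not close the gap, because section 15 places no time limit on the ground and section 12 does not require the call. The bias argument needs no difference between arms in ability to travel. It needs only discretion exercised by people who may know the allocation.

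A reader might go further in three ways that the documents do not support:
- *That section 4 bars the very women for whom the telephone route was written.* Section 12 fits enrolled women who planned to return and could not.
- *That the entry criterion no longer serves data quality and should be relaxed to admit women known to be reachable only by telephone.* Clinic visits still serve the culture-based UTI definitions in Aims 1 and 2, one of which needs no symptoms, and the SSI criteria, which rest on wound findings, clinician diagnosis, culture or imaging.
- *That the number of women affected can be read from the planned 20% loss (20% × 200 = 40).* The plan does not say what share of losses would be women unable to attend, or how often staff would withdraw them.

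**Conclusion.** The point holds as a defect in section 15, made worse by the optional wording in section 12 and the clinic-only wording in section 8. It is not a contradiction between sections 4 and 12. As written, the plan permits discretionary removal after randomisation of women whose 2-week UTI status could be obtained by telephone, at least for the empirically treated component of Aim 1 and for care received elsewhere.

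The number of women affected cannot be estimated from the documents. The 1.2 to 4.9 point shifts show only sensitivity: they assume 58 per arm, UTI rates of 10% to 33%, and one to three removals of women with UTI, all from one arm. They are not a prediction that this will happen. The recruitment target is not threatened. The matter merits an amendment because it touches the primary outcome and is cheap to close.

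**What to change.** Reconcile sections 4, 8, 12 and 15:

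- **Section 4:** keep the criterion, and state that it is judged only before randomisation.
- **Section 15:** state that inability to attend after randomisation is not a ground for withdrawal, either as an exclusion criterion met later or as failure to follow the protocol. Other grounds for withdrawal are outside this point.
- **Section 12:** replace the optional call with a commitment to telephone every randomised woman who does not attend, at 2 and at 6 weeks, unless she has withdrawn consent. Record for each outcome whether it came from clinic, culture or telephone.
- **Section 8:** amend the clinic-only sentence to match.
- **Section 13:** state that these women are analysed in the group to which they were randomised.

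The cost is a few sentences in an amendment and some coordinator time. Section 21 already provides for telephone interviews for study data gathering, and every participant must have a telephone. The downside is that a call is less sensitive than examination or culture, especially for SSI, and lower sensitivity can shrink a true difference between arms. Recording the source allows the share of telephone outcomes to be reported by arm.
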